  - a) Chronic liver disease, liver function test abnormalities or other signs of hepatic insufficiency (ALT, AST, total bilirubin > 1.5 x ULN)
  - b) Respiratory insufficiency

- c) Renal insufficiency defined as eGFR <45 mL/min based on the CKD-EPI formula,  

- d) Heart disease (myocardial infarction, unstable angina, heart failure, cardiomyopathy within six months before screening)
- e) Bradycardia (<45/min.) or tachycardia (>100/min.)
- f) Poorly managed hypertension (systolic >160 mm Hg and/or diastolic >95 mm Hg) or hypotension (systolic <90 mm Hg and/or diastolic <60 mm Hg)
- g) Uncontrolled diabetes defined by glycosylated hemoglobin (HbA1c) >7.5%
- 8) History of cancer within 3 years of screening with the exception of fully excised non-melanoma skin cancers or non-metastatic prostate cancer that has been stable for at least 6 months.
- 9) Seropositive for human immunodeficiency virus (HIV).
- 10) History of acute/chronic hepatitis B or C and/or carriers of hepatitis B (seropositive for Hepatitis B surface antigen [HbsAg] or anti-Hepatitis C [HCV] antibody).
- 11) Clinically significant abnormalities in screening laboratory tests, including:
  - a) hematocrit less than 33% for males and less than 30% for females
  - b) absolute neutrophil cell count of 1200/uL (with the exception of a documented history of a chronic benign neutropenia), or platelet cell count of <120,000/uL
  - c) INR >1.4 or other coagulopathy, confirmed by repeat.
- 12) Disability that may prevent the patient from completing all study requirements (e.g. blindness, deafness, severe language difficulty, etc.).
- 13) Women who are fertile and of childbearing potential.
- 14) Within 4 weeks of screening visit or during the course of the study, concurrent treatment with antipsychotic agents (except risperidone  $\leq 1.5$  mg/day, quetiapine  $\leq 100$  mg/day, olanzapine  $\leq 5$  mg/day, and aripiprazole  $\leq 10$  mg/day), antiepileptics (except lamotrigine, gabapentin and pregabalin for nonseizure indications), centrally active anti-hypertensive drugs (e.g., clonidine, l-methyl dopa, guanidine, guanfacine, etc.), opiate analgesics, systemic corticosteroids, psychostimulants, antiparkinsonian medications (except for non-parkinsonian indications) and mood stabilizers (e.g., valproate, lithium), sedatives and anxiolytics with the exception that use of short- to medium-acting benzodiazepines for treatment of insomnia is permitted,

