#### **15.1.6 12-lead Electrocardiogram**

ECGs will be recorded using a digital ECG to provide machine-generated interval measurements. The Bazett formula should be utilized for QTc interval correction:

$$QT_c = \frac{QT}{\sqrt{RR}}$$

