8. SAFETY DATA

8.1. Safety Assessments

Safety assessments are as follows:

- Adverse events and concomitant medications used:
 - Continuous monitoring throughout the study period
- Vital signs:
 - Body temperature, seated systolic and diastolic BP, pulse rate and respiratory rate
- Body mass
- Clinical laboratory tests:
 - Hematology - red blood cell count, erythrocyte mean corpuscular haemoglobin concentration (MCHC), erythrocyte mean corpuscular volume (MCV), hematocrit, hemoglobin, leukocyte count, and absolute counts of monocytes, neutrophils, basophils, eosinophils and platelets
 - Chemistry - glucose, calcium, albumin, total protein, sodium, potassium, bicarbonate, chloride, magnesium, BUN, creatinine, creatine kinase, alkaline phosphatase, ALT, AST, bilirubin, lipase, lactate dehydrogenase (LDH) and phosphorus
 - Coagulation –INR, prothrombin time.
 - Urinalysis – osmolality, creatinine, calcium, sodium, turbidity, color, specific gravity, pH, protein, glucose, ketones, bilirubin, blood, urobilinogen, nitrite, leukocytes, and microscopic particles
 - Thyroid Tests – TSH, T3, T4
- ECG (ventricular rate, PR, QRS, QT, QTcF (Fridericia's formula for correction), QTcB (Bazett's formula for correction))
- Physical examination including all major organ systems (exception: genitourinary and reproductive should be symptom-directed).
- Symptom Directed Neurological Examination
- Columbia Suicide Severity Rating Scale (C-SSRS)

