ECG parameters will be listed and summarised by treatment and study time point. A summary of changes from pre-dose baseline will also be presented. For QTcB the number of subjects with values greater than 450 (and 480, 500) msec or an increase from baseline of at least 30 (and 60) msec will also be presented, in accordance with ICH E14 (Note for guidance on the clinical evaluation of QT/QTc interval prolongation and proarrhythmic potential for non-antiarrhythmic drugs, CHMP/ICH/2/04).

Changes in physical examination findings over time will be listed by body system for each subject. It is noted that any untoward findings identified on physical examinations after the administration of the first dose of study medication will be captured as an adverse event if those findings meet the definition of an adverse event as defined in the protocol.

Changes in neurological examination findings over time will be listed by neurological system for each subject.

Changes in the Columbia Suicide Severity Rating Scale (C-SSRS) will be listed for each subject.

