14.3.6 ECG Parameters

- Table 14.3.6.1 Summary of ECG Parameters (Ventricular Rate) by Treatment
- Table 14.3.6.2 Summary of ECG Parameters (PR Interval) by Treatment
- Table 14.3.6.3 Summary of ECG Parameters (QRS Duration) by Treatment
- Table 14.3.6.4 Summary of ECG Parameters (QT Interval) by Treatment
- Table 14.3.6.5 Summary of ECG Parameters (QTcF) by Treatment
- Table 14.2.6.6 Summary of ECG Parameters (QTcB) by Treatment
- Table 14.3.6.7 Summary of Derived Categorical QTcB by Treatment

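### QTc outlier counts are planned for Bazett only, although Fridericia is already in the SAP; heart rate alone can change who is counted

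*SAP*

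**What the plan says.** SAP 8.1 carries both corrections as ECG parameters: "QTcF (Fridericia's formula for correction), QTcB (Bazett's formula for correction". SAP 8.2 lists all ECG parameters and summarises them by treatment and time point, with changes from baseline.

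The categorical analysis is narrower. SAP 8.2 reads "For QTcB the number of subjects with values greater than 450 (and 480, 500) msec" and continues "or an increase from baseline of at least 30 (and 60) msec will also be presented". Both the absolute and the change categories therefore apply to QTcB alone.

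SAP Appendix 2, section 14.3.6, matches this. QTcF has a descriptive table, 14.3.6.5 ("Summary of ECG Parameters (QTcF) by Treatment"). The only outlier table is 14.3.6.7 ("Summary of Derived Categorical QTcB by Treatment"). No reason is given for leaving QTcF out of the categories.

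Protocol 15.1.6 is the source of the choice: "The Bazett formula should be utilized for QTc interval correction". The protocol does not name Fridericia.

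**The concern.** The two corrections agree only at 60 beats per minute. Away from that rate, a fixed cut on QTcB corresponds to a different QTcF at each heart rate, and a shift in heart rate on treatment moves QTcB relative to QTcF. A participant can enter or leave the outlier table for that reason alone.

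Safety is the primary objective, and change in ECG findings is part of the primary endpoint (protocol 6.2.1). About 7 participants are planned per arm (protocol 17.2), so one participant is 1/7, or 14%, of an arm. Readers are likely to look at counts, because means in groups of that size are imprecise. Protocol 4.2.3 also reports two hERG assays with mean IC50 values of 26 and 0.6 µM, a difference it leaves unexplained. The same section reports no ECG effects in two dog studies up to mean Cmax values of about 4 µM. The question is open and no hazard is established, which is a reason to make the clinical display robust to the choice of formula.

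**Working it through.** There is no figure in the plan to reproduce. The check is how far the two corrections diverge over the heart rates that entry allows.

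**Inputs**
- Bazett, as printed in protocol 15.1.6: QTcB = QT/RR^(1/2), with RR = 60/HR in seconds.
- Fridericia, named in SAP 8.1 and taken in its standard form: QTcF = QT/RR^(1/3).
- Categories from SAP 8.2: above 450, 480 and 500 msec; increase of at least 30 and 60 msec.
- Heart-rate range, from the exclusion in protocol 9.3 ("Bradycardia (<45/min.) or tachycardia (>100/min"): 45 to 100 beats per minute at entry.
- The QT and QTcF values used below are assumptions for illustration.

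**Ratio.** QTcB/QTcF = RR^(1/3 − 1/2) = RR^(−1/6) = (HR/60)^(1/6).

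**Absolute cuts.** Dividing each QTcB cut by the ratio gives the QTcF at which a participant crosses it:

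| HR (beats/min) | QTcB/QTcF | QTcB 450 | QTcB 480 | QTcB 500 |
|---|---|---|---|---|
| 45 | 0.953 | 472 | 504 | 525 |
| 50 | 0.970 | 464 | 495 | 515 |
| 60 | 1.000 | 450 | 480 | 500 |
| 80 | 1.049 | 429 | 458 | 477 |
| 100 | 1.089 | 413 | 441 | 459 |

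Across the entry range, the 450 msec cut spans 472 − 413 = 59 msec on the QTcF scale.

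Two hypothetical tracings at the limits of the range:
- HR 100, RR 0.600 s, QT 350 msec: QTcB = 350/0.600^(1/2) = 451.8, counted above 450. QTcF = 350/0.600^(1/3) = 415.0, not above 450.
- HR 45, RR 1.333 s, QT 500 msec: QTcB = 500/1.333^(1/2) = 433.0, not counted. QTcF = 500/1.333^(1/3) = 454.3, above 450.

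**Change categories**
- Hold QTcF at 420 msec and start from 60 beats per minute, where QTcB is also 420. QTcB reaches 450 when (HR/60)^(1/6) = 450/420, so HR = 60 × (450/420)^6 = 90.8. A rise to about 91 beats per minute alone therefore meets the 30 msec category.
- For a rise from 60 to 90 beats per minute with QTcF held constant, the QTcB increase is 28.0, 29.4 and 30.8 msec at QTcF 400, 420 and 440.
- In the other direction, let QTcF rise from 420 to 450 while HR falls from 75 to 60. The ratio at 75 is 1.0379, so QTcB goes from 435.9 to 450.0. The 30 msec increase in QTcF shows as 14.1 msec in QTcB and is not counted.

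**What cannot be computed.** The documents give no distribution of heart rate or QT, so the number of participants reclassified is unknown and could be zero.

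**The case against.** The strongest reply is that the SAP does what the protocol tells it to do. Protocol 15.1.6 names Bazett and the outlier table uses Bazett. That stands: the two documents do not contradict each other, and the SAP already goes further by adding QTcF.

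Second, QTcF is not lost. It has its own summary table, and ECG values and changes are listed by subject in Listings 16.2.9.3 and 16.2.9.4. The visit text in protocol 10.2 gives about seven scheduled ECGs per participant in the primary study (visits 1, 2, 4, 7, 8, 11 and 12). For 21 participants that is about 147 records, few enough to read through. This also stands, but counts by arm built that way would be made after unblinding and would not be prespecified.

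Third, nothing turns on the table formally. Safety analyses are descriptive (SAP 8.2), and the stopping rules in protocol 7.3.1 contain no QTc threshold. This limits the consequence.

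A reader might go further and infer that Bazett wrongly flags participants at fast rates and misses true outliers at slow ones. The documents do not support that. They name no reference correction other than Bazett, and the algebra shows only that the two formulas diverge, not which is right. SAP 8.2 cites ICH E14 for its categories, but what that guidance says about correction formulas lies outside the documents and is not used here.

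**Conclusion.** The point holds as a limitation of one prespecified safety output. The outlier counts rest on a single correction, and they can differ from Fridericia counts because of heart rate alone. Over the entry range the 450 msec QTcB cut corresponds to QTcF values from 472 down to 413 msec, and a plausible heart-rate shift can create or hide a 30 msec change.

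This rests on the standard Fridericia formula and on treating 45 to 100 beats per minute as the relevant range. That range is an entry limit, not an on-treatment limit. The worked tracings sit at its edges, with QT values chosen to straddle the cut, so they illustrate the mechanism and do not estimate its frequency.

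It would be too strong to say that the QT conclusion of this trial would change, or that the hERG results point to a clinical QT effect. The first cannot be computed from the documents. The second would ignore the dog findings in the same protocol section. The case for acting is that a count within the primary safety endpoint becomes less dependent on the choice of formula at almost no cost.

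**What to change.** - In SAP 8.2, apply the same absolute categories (above 450, 480 and 500 msec) and change categories (at least 30 and 60 msec) to QTcF as well as QTcB.
- In SAP Appendix 2, section 14.3.6, add a categorical QTcF table beside Table 14.3.6.7, and keep the QTcB table as the output for the protocol-specified correction.
- State in SAP 8.2, before unblinding, which correction leads the interpretation when the two disagree, and refer to protocol 15.1.6 so that the relation to the named formula is explicit.

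The cost is one extra table and a few sentences. QTcF is already among the planned parameters, so no new data are needed and no existing output is lost.

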9. EFFICACY DATA

9.1. Efficacy Assessments

Efficacy is assessed by the cognitive and clinical outcomes ADAS-Cog, NTB, ADCS-ADL, MMSE, CDR-SB and ADCS-CGIC scales, measured at the following timepoints:

- V1 (Study Day -60 to -1)/Step 1 (MMSE only)
- Baseline V2 (Study Day 1) (excluding MMSE)
- V5 (Study Day 43)
- V7 (Study Day 85)
- V9 (Study Day 127)
- Final/Early Discontinuation V11 (Study Day 169) (for subjects participating in the Primary Study Only)
- V11 (Study Day 169) (for subjects participating in the Extension Study)
- V13 (Study Day 253) (for subjects participating in the Extension Study)
- Final/Early Discontinuation V15 (Study Day 337) (for subjects participating in the Extension Study)

9.2. Efficacy Data Presentation

All cognitive and clinical assessments for each subject will be presented in individual data listings.

For the ADAS-Cog (sub) scales, the total score for the corresponding items will be calculated as per Section 5.5. The total score and the Change from Baseline in the total score will be included in the individual data listings. Both the total score and the change from baseline will be summarized by visit and treatment group. Observed Mean change from Baseline (+/- SD) in ADAS-Cog total scores will be presented graphically by treatment group over time.

For NTB, the total time (in seconds) taken to complete both Trail A and Trail B will be presented in the same way as for the ADAS-Cog total score, as described above.

The total score for ADCS-ADL, for MMSE and for CDR-SB will be presented in the same way as for the ADAS-Cog total score, as described above.

The Composite z-score scales will be presented for each scale, in the same way as for the ADAS-Cog total score, as described above.

For ADCS-CGIC, the individual data listing will present the original score on the seven-point scale. In addition, the seven-point score will be collapsed to 3 groups, combining scores 1-3 to "Improved", 4 to "No change", and 5-7 to "Worsening". This derived three-point scale will also be included in the individual data listing.

For the seven-point scale and the derived three-point scale, the number of subjects in each of the categories will be summarized by visit and treatment group using counts and percentages.

9.3. Efficacy Analysis

The change from baseline in the composite scores and clinical outcomes will be analyzed using a mixed effects model including fixed effects for treatment group (i.e. 300 mg active, 100 mg active, placebo), visit and treatment by visit interaction. In addition, the subject's baseline score will be included as a covariate. For each time point up to and

including 6-months, the treatment differences between 300 mg active and placebo, and 100 mg active and placebo will be estimated from the model. In addition, the low and high CT1812 dosed groups will be pooled and compared with the placebo group. This analysis will be considered the primary analysis.

A separate pooled analysis and analysis by arm will also be performed for time points up to and including the 12-month time point.

Additionally, p-values and corresponding two-sided confidence intervals will be provided. The LS Mean Change from Baseline in ADAS-Cog total scores with 95% CI will be presented graphically by treatment group over time.

In the event that a scale or parameter only has a single post-baseline timepoint, an ANCOVA model will be run in place of the MMRM model without the visit and visit by treatment interaction terms. The ANCOVA model will include a fixed effect for treatment group, and the subject's outcome at baseline as a covariate. For parameters for which there are multiple post-baseline timepoints, ANCOVA models such as that just described above may also be run in addition to the MMRM model at various timepoints.

The change from baseline in the ADAS-Cog (sub) scale total score, total time (in seconds) taken to complete both Trail A and Trail B in the NTB, ADCS-ADL total score, MMSE, CDR-SB, and composite scores will be analysed using the MMRM model described above.

To compare 300 mg active vs placebo and 100 mg vs placebo statistically, observed values for ADCS-CGIC will be analyzed using the MMRM model described earlier without the baseline term. Additionally, frequencies and percentages in the ADCS-CGIC will be summarized by visit. Cochran-Mantel-Haenszel mean score statistics, using rank scores will be used to assess the difference in ADCS-CGIC responses at each visit between the CT1812 dose levels and placebo.

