#### **6.2.2 Secondary Endpoints**

The primary imaging endpoint is the change from the baseline in synaptic density as measured by differences in SV2A PET ligand C-UCB-J uptake after dosing with CT1812 versus placebo.

Cognitive and clinical outcomes:

- Mini Mental State Exam (MMSE).

- Alzheimer's Disease Assessment Scale-Cognitive Subscale (ADAS-Cog) 11 and ADAS-Cog13 (delayed recall and Number Cancellation added to ADAS-Cog11 in the ADAS-Cog13); ADAS-Cog14 includes the maze added to ADAS-Cog13.
- Neuropsychological Test Battery (NTB) including Trails A and B, Digit Span, and Letter and Category Fluency (CFT).
- Alzheimer's Disease Cooperative Study (ADCS)-Clinical Global Impression of Change (CGIC).
- ADCS-Activities of Daily Living (ADCS-ADL).
- Clinical Dementia Rating Scale – Sum of Boxes (CDR-SB)
- Composite z-score scales (Cognitive Composite score; Memory composite score; Attention composite score; Executive Function composite score).
- Imaging Outcomes
  - FDG PET
  - Functional MRI
  - Volumetric MRI
- CSF pharmacodynamics in AD patients through measurement of CSF A $\beta$  40, A $\beta$  42, A $\beta$  oligomers, tau, phospho-tau, neurogranin, SNAP25, and NFL.

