### **16.5 Neuropsychological Test Battery (NTB)**

The NTB (Harrison et al, 2007) is a neuropsychological test battery that in this study includes Trails A & B, Digit Span, and Category Fluency. The NTB may be more sensitive than the ADAS-Cog in assessing patients with mild to moderate AD and may have particular utility in drug studies.

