Trail Making Test (TMT) A – This is essentially a measure of attention, as successful completion relies on quickly and accurately connecting numbered circles in an ascending sequence. The key metric for analysis purposes is ‘Time taken for completion’. Errors and time taken once again both contribute to performance. However, because errors incur a time penalty, it is not necessary to analyze both metrics. The sign of the z-score for this component will be reversed when deriving the Cognitive Composite score.

TMTB – This is the more complex component of the TMT in which successful completion relies on the study participant accurately connecting the numbered and lettered circles. Study participants are required to alternate between numbers and letters in an ascending sequence. The key metric for analysis purposes is again ‘Time taken for completion’. As with TMT A, because errors incur a time penalty, it is not necessary to factor in errors for analysis purposes. The sign of the z-score for this component will be reversed when deriving the Cognitive Composite score.

- The Memory composite score will be a composite z-score average similar to the Cognitive Composite score, but will only be derived using the average of the

ADAS-Cog Word Recall, Orientation, Delayed Word Recall, and Word Recognition items. If a subject is missing any of the four items at a timepoint, this composite score will not be derived.

- The Attention composite score will be a composite z-score average derived using the average of the Number Cancellation, Maze item from ADAS-Cog 14, and TMT A items. If a subject is missing either of the three items at a timepoint, this composite score will not be derived.
- The Executive function composite score will be a composite z-score average derived using the average of the CFT, Digit Span, and TMT B items. If a subject is missing any of the three items at a timepoint, this composite score will not be derived.

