11.8. Changes from the Analysis Planned in the Protocol

There are no changes from the planned analysis described in the protocol.

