- Table 14.2.4.34 Individual Total Scores for Mini Mental State Exam (MMSE)
- Table 14.2.4.35 Summary of Total Score for Mini Mental State Exam (MMSE)
- Figure 14.2.4.36 Mean Change from Baseline in Total Score for Mini Mental State Exam (MMSE) Over Time
- Table 14.2.4.37 Analysis of Change from Baseline in Total Score for Mini Mental State Exam (MMSE), up to 6-months
- Figure 14.2.4.38 LS Mean Change from Baseline in Total Score for Mini Mental State Exam (MMSE) Over Time, up to 6-months
- Table 14.2.4.39 Analysis of Change from Baseline in Total Score for Mini Mental State Exam (MMSE), up to 12-months
- Figure 14.2.4.40 LS Mean Change from Baseline in Total Score for Mini Mental State Exam (MMSE) Over Time, up to 12-months
- Table 14.2.4.41 Individual Total Scores for Clinical Dementia Rating Scale – Sum of the Boxes (CDR-SB)
- Table 14.2.4.42 Summary of Total Score for Clinical Dementia Rating Scale – Sum of the Boxes (CDR-SB)
- Figure 14.2.4.43 Mean Change from Baseline in Total Score for Clinical Dementia Rating Scale – Sum of the Boxes (CDR-SB) Over Time
- Table 14.2.4.44 Analysis of Change from Baseline in Total Score for Clinical Dementia Rating Scale – Sum of the Boxes (CDR-SB), up to 6-months

- Figure 14.2.4.45 LS Mean Change from Baseline in Total Score for Clinical Dementia Rating Scale – Sum of the Boxes (CDR-SB) Over Time, up to 6-months
- Table 14.2.4.46 Analysis of Change from Baseline in Total Score for Clinical Dementia Rating Scale – Sum of the Boxes (CDR-SB), up to 12-months
- Figure 14.2.4.47 LS Mean Change from Baseline in Total Score for Clinical Dementia Rating Scale – Sum of the Boxes (CDR-SB) Over Time, up to 12-months
- Table 14.2.4.48 Summary of Alzheimer's Disease Clinical Study – Clinician Global Impression of Change (ADCS-CGIC)
- Table 14.2.4.49 Analysis of Alzheimer's Disease Clinical Study – Clinician Global Impression of Change (ADCS-CGIC), up to 6-months
- Table 14.2.4.50 Analysis of Alzheimer's Disease Clinical Study – Clinician Global Impression of Change (ADCS-CGIC), up to 12-months
- Table 14.2.4.51 Frequency table for Alzheimer's Disease Clinical Study – Clinician Global Impression of Change (ADCS-CGIC)
- Table 14.2.4.52 Individual Scores for Composite z-score scales (Cognitive, NTB, Memory, Attention, Executive Function)
- Table 14.2.4.53 Summary of Scores for Composite z-score scales (Cognitive, NTB, Memory, Attention, Executive Function)

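### The stand-alone NTB analysis covers only Trail A plus Trail B time, the planned NTB composite is undefined, and no rule covers a Trail left unfinished for cognitive reasons

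*SAP*

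**What the plan says.** **What the battery is.** Protocol 6.2.2 lists as a secondary endpoint the "Neuropsychological Test Battery (NTB) including Trails A and B, Digit Span, and Letter and Category Fluency (CFT"), and SAP 4.6 repeats this. Protocol 16.5 describes the battery as "Trails A & B, Digit Span, and Category Fluency", without Letter Fluency.

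**What is analysed under the NTB label.** SAP 9.2 states: "For NTB, the total time (in seconds) taken to complete both Trail A and Trail B will be presented". SAP 9.3 enters the same variable, the "total time (in seconds) taken to complete both Trail A and Trail B in the NTB", in the mixed model for repeated measures (MMRM), and Tables 14.2.4.20 to 14.2.4.26 follow it. Appendix 2 also plans listings, summaries and inferential tables (14.2.4.52 to 14.2.4.58), beginning with "Individual Scores for Composite z-score scales (Cognitive, NTB, Memory, Attention, Executive Function"). SAP 5.5 defines the Cognitive, Memory, Attention and Executive composites but no NTB composite. SAP 12.2 mentions an NTB total score for graphs, also undefined.

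**Where the other tests go.** Under SAP 5.5, Category Fluency, Digit Span, Trail A and Trail B are four of the ten Cognitive Composite items. Category Fluency, Digit Span and Trail B form the Executive composite, and Trail A is one of three Attention items. SAP 9.3 models all these composites. SAP 9.4 uses the individual NTB items in correlations.

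**Missing values.** The Trail metric is completion time. For the Executive composite: "If a subject is missing any of the three items at a timepoint, this composite score will not be derived". The Attention composite has an equivalent rule. In the Cognitive Composite, one to three missing items are replaced by the mean z-score of all subjects with a value at that timepoint. SAP 5.6 considers whether an item is missing for non-cognitive reasons only for the ADAS-Cog totals. It then allows no further efficacy imputation and relies on missing at random. SAP 11.8 states: "There are no changes from the planned analysis described in the protocol".

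**The concern.** There are two linked problems.

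First, the SAP does not settle what the NTB outcome is. The variable it specifies in full is a Trail-time total. The variable that would represent the battery appears only in table titles, so components, signs and missing-item rule would have to be chosen at programming, possibly with the data in view.

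Second, a completion time exists only for a person who completes the test. In participants with MMSE 18-26, failure to finish Trail B is plausibly a sign of poor function rather than an unrelated gap. If the case report form then holds no time, the stated rules either drop that result or score the person as average. Missing at random is least credible where the reason for the missing value is the poor performance itself. At stake are the NTB, Executive and Cognitive Composite results, and the Attention result if Trail A is the unfinished test.

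**Working it through.** The plan states no figure for this point, so there is none to reproduce.

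**Step 1. Coverage of the named battery.**

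| Test (Protocol 6.2.2, SAP 4.6) | In Protocol 16.5 | In the A+B total | In a defined, modelled composite |
|---|---|---|---|
| Trail A | yes | yes | Cognitive, Attention |
| Trail B | yes | yes | Cognitive, Executive |
| Digit Span | yes | no | Cognitive, Executive |
| Category Fluency | yes | no | Cognitive, Executive |
| Letter Fluency | no | no | none |

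The A+B total covers 2 of 5 tests (2/5 = 40%), or 2 of 4 under Protocol 16.5. The defined composites cover 4 of 5.

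**Step 2. Follow one participant who attempts Trail B, cannot finish for cognitive reasons, and has no time recorded.**

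- A+B total: missing at that visit. A valid Trail A time does not contribute to this variable.
- Executive composite: not derived at that visit.
- Cognitive Composite: Trail B is filled with the mean z-score of everyone who has a value, pooled over arms. The composite is the mean of ten items, so it is shifted by (fill value − the participant's own Trail B z-score)/10. If the person is worse than average, the shift is favourable.
- If this happens at baseline: Protocol Table 1 and SAP 9.1 give only one pre-dose NTB assessment, at Visit 2. There is then no baseline value, hence no change score for the A+B total or the Executive composite at any visit.
- If it happens only after baseline: the MMRM keeps the participant's other visits and treats the lost one as missing at random.

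**Step 3. Illustrative size.** Inputs: 21 participants, 7 per arm (Protocol 17.2). The share q who cannot finish is not in the documents, so the range is an assumption. Expected number affected = 21q. Chance that a given arm has at least one = 1 − (1 − q)^7.

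| q (assumed) | 21q | At least one in an arm of 7 |
|---|---|---|
| 10% | 2.1 | 1 − 0.9^7 = 52% |
| 20% | 4.2 | 1 − 0.8^7 = 79% |
| 30% | 6.3 | 1 − 0.7^7 = 92% |

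One non-finisher is 1/7 = 14% of an arm at that visit.

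**The case against.** The strongest reply is that most of the battery is analysed. Four of the five tests enter composites that are secondary endpoints and go through the MMRM, and Digit Span and Category Fluency make up two of the three Executive items. This stands. A reader who saw only SAP 9.2 and 9.3 might infer that the NTB is examined solely as a Trail total, or that a non-finisher's Trail A time is thrown away. Neither is so: Trail A remains in the Attention and Cognitive composites, and Table 14.2.4.20 shows individual Trail times.

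The second reply is that an unfinished Trail may already receive a value. The key to Protocol Table 1 provides for central scoring, and SAP 5.5 says that errors cost time, which points to administration rules outside these documents. A maximum time may exist there. This also stands: it cannot be asserted that a non-finisher has no value, only that neither document gives a code. If a cap is already applied, step 2 does not occur and a sentence in the SAP suffices.

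Third, a reader might infer a bias toward no effect. That would need more non-finishers on placebo. With more on active drug, the same rules would hide harm. Nothing in the documents fixes the direction.

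Fourth, a reader might take the SAP 11.8 statement as false. Protocol 17.4 and 17.6 commit to the composite scores and to a selection of the clinical measures, and the protocol defines no NTB summary score. Using Trail time is therefore not a clear departure. The undefined composite and the unscored Letter Fluency remain gaps all the same.

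Finally, the NTB is one of many secondary outcomes in a pilot whose primary objective is safety, and SAP 5.5 names ADAS-Cog11, which contains no Trail item, as the primary cognitive endpoint. This limits the weight of the point but does not answer it.

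**Conclusion.** The point holds in three parts. The stand-alone NTB variable represents 2 of the 5 named tests, while the NTB composite planned in Appendix 2 has no definition. Letter Fluency is named as part of an endpoint but is scored nowhere. No code is given for a Trail unfinished for cognitive reasons, and if no time is recorded the written rules drop that result or replace it with an average one.

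The first two parts rest on the text alone. Reading the A+B variable as a sum is the natural reading, though no formula is given. The third is conditional on no cap being applied in scoring. Its size rests on an assumed 10-30% non-completion, about 2 to 6 of 21 participants per visit, and its direction depends on the balance of non-finishers between arms. The SAP should be changed before analysis; the primary safety objective is not affected.

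**What to change.** 1. In SAP 5.5, define the NTB composite as the mean z-score of Trail A, Trail B, Digit Span and Category Fluency, with signs aligned so that higher is better. Give it a missing-item rule; requiring all items, as the Executive composite does, would be consistent. Analyse it as the NTB endpoint.
2. If Letter Fluency is collected, score it and include it. If not, delete it from Protocol 6.2.2 and SAP 4.6.
3. Model Trail A and Trail B separately rather than as a total.
4. Code a Trail attempted but not finished for cognitive reasons at a maximum time fixed in advance, taken from the administration rules if they set one. Apply the code in the Trail, NTB, Executive, Attention and Cognitive Composite analyses, and say whether capped values enter the baseline mean and SD used for z-scores. Keep missing for non-cognitive reasons.
5. Add a sensitivity analysis that treats unfinished Trails as missing, and tabulate non-completion by arm and visit.
6. Record the changes in SAP 11.8.

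The cost is SAP text and a small amount of programming, with no new data provided that the reason for non-completion was recorded. The drawbacks are some ceiling values in Trail time, and an NTB composite that shares three items with the Executive composite, so the two are not independent evidence.
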